8.5.2 Blinding

Subjects in the randomized cohort will be blinded to the Study Arm to which they are randomized.

Site personnel will not be informed of the specific Study Arm assignment (they will only know the treatment # assigned); those administering the treatment will observe the treatment effect and the disposal process and may be unblinded as a result of their observations. This person will not conduct the follow-up assessments. These personnel will be instructed and trained not to reveal the assumed Study Arm assignment to any subject or to any of the other study personnel at the site. Site personnel completing follow-up evaluations will be different from the person who conducted the procedure and, therefore, will be blinded to the subject's treatment.

Subjects will be instructed (by subject handout Appendix G) not to discuss their assumed treatment assignment with anyone at the study site.

Only necessary persons at the sponsor shall know the treatment assignments and only those persons will have access to the database which holds the key for the treatment numbers distributed at each site. All others at the sponsor will remain blinded.

CANDESANT BIOMEDICAL	CLINICAL STUDY PROTOCOL SAHARA STUDY	Document #: CB-CLP-001 Revision: E
---------------------------------	---	---------------------------------------

8.6 Enrollment

As described above, subjects will be considered enrolled if they have given informed consent, they meet the study eligibility criteria upon assessment at both screening and baseline, and they are treated as part of the Roll-In Cohort or undergo randomization. A schematic overview of the subject enrollment process is shown in **Figure 2**.

Enrolled subject will be entered into the study database. Upon entering the subject into the study database, a unique subject ID will be assigned to the subject by the electronic system.

[figure not shown]
The unique subject ID that is assigned will be based upon the information entered by the study site. In summary, the subject ID will be assigned as follows: Sahara study identifier (SAH), followed by the 3-digit site ID (XXX), a 3-digit unique subject ID (a consecutive number determined by the electronic system from the number of patients enrolled at the time the subject is added), followed by the subjects initials (YY) (defined as first letter of first name then first letter of last name), i.e., SAH-XXX-001YY, SAH-XXX-002YY, etc.

Once the subject is added and the unique subject ID is assigned, the subject will be automatically assigned to the roll-in cohort, or, randomized and assigned a treatment number as explained above.

The site will maintain a Subject Screening Log, which will link the unique subject ID to the subject. This log will remain confidential and will not be provided to the sponsor, but, will only be used for reference during monitoring at the study site.

8.6.1 Screen Failures

If the subject has consented, but becomes ineligible prior to enrollment, the reason for ineligibility will be documented on the Screening Log. A copy of the subject's consent will be maintained in the site's study records. Ineligibility may occur at the screening visit, at the baseline visit or prior to randomization. Once a subject is randomized; they are enrolled. Treatment with the assigned treatment number should be conducted.

Figure 2: Enrollment Flowchart, Initial Screening through Treatment

8.7 Procedure

The Candesant N-SWEAT Patch is intended for use only by appropriately trained personnel. All investigators and support staff will be provided comprehensive training by Candesant Biomedical (or their designee) in the handling, use, and disposal of the patch. Treatment will be performed in a clinic or doctor's office, by a trained medical professional.

8.7.1 Immediately Pre-Treatment

The following baseline evaluations will be performed immediately prior to treatment, in the following order.

Treatment Site Identification: The target treatment area should be chosen by identifying a relatively flat area with the highest concentration of hair follicles. This placement is intended to maximize contact with the location of sweat production. The planned treatment site may be marked for convenience.

Treatment Site Assessment: Although an assessment should have been conducted prior to randomization; the planned treatment area(s) should be inspected a final time to ensure the planned site meets treatment requirements as outlined in the N-SWEAT Patch Instructions for use (IFU). The area must be free of residue, and free of

CANDESANT BIOMEDICAL	CLINICAL STUDY PROTOCOL SAHARA STUDY	Document #: CB-CLP-001 Revision: E
-------------------------	---	---------------------------------------

abrasions, broken skin, or other conditions of concern. The assessment should include both visual and tactile assessment of any irregularities.

Note: *Areas with skin tags, moles or other skin abnormalities that are not indicative of abraded skin are permissible for treatment. At the discretion of the treating physician the area may be avoided with strategic patch placement and/or use of an adhesive strip.*

Note: *If skin irritation is noted, it should be assessed in accordance with the Erythema and Clinical Signs/Symptoms (Appendix B). If irritation greater than 1 is observed, the subject may only be treated after the issue has been resolved (less than or equal to 1).*

Hair removal by clipping or shaving should NOT be done within 72 hours prior to the procedure. If the planned area does not meet the IFU requirements, do not proceed with treatment. If the operator has questions or concerns regarding the treatment site, the sponsor should be contacted for consultation before moving forward with the procedure.

Treatment Site Preparation: The subject's axilla will be cleaned with alcohol to ensure that no residual deodorant / anti-perspirent or other residue remains in the target treatment area. The area shall then be thoroughly dried.

Photos: Pre-treatment photos are to be taken of each axilla and maintained by the study site as a baseline reference in the event that an adverse skin reaction should occur or another matter necessitating review for patient safety. Photos are to be taken with a high-resolution camera with the arm in the standardized treatment position and adequately illuminated. Photos are to be marked with Subject ID, date and subject side (i.e. Right or Left). Photos are to be taken with a measurement calibration reference visible.

8.7.2 Patch Application

An overview of the patch application procedure is provided below; however, it is critical to reference the IFU provided for additional treatment and handling details.

Per the IFU, all personnel involved in the handling of the provided patch must have gloved hands at all times.

The patch will be placed on the target treatment area (as previously described). If the subject reports any pain or uncomfortable sensation at the time of patch placement; the patch should be immediately removed.

Upon placement of the patch, the timer shall be started. Every 30 seconds, the subject shall report their pain level on a score of 1 to 10. If the subject reports a pain level greater than 8 or shows a 8 or higher using the Wong-Baker FACES pain scale (**Figure 3**); the patch should be removed immediately regardless of the time that the patch has been in place.

Figure 3. Wong-Baker FACES® Pain Rating Scale

Wong-Baker FACES® Pain Rating Scale

If the timer reaches 3 minutes and the patch is still in place, it should be removed at the 3 minute mark. The actual treatment duration should be documented in the subject's study record. The procedure may be photographed or videotaped (provided the subject has consented to video/photography). The subject's identity will be concealed, and subject confidentiality will be maintained at all times.

NOTE: In the event of excessive exposure to the N-SWEAT patch or insufficient cleaning post treatment, an alkaline or thermal burn is possible. Acute burns are treated by flushing with water for 30 minutes followed by routine skin and wound care (Sander, 2011). Please have water and gauze available at all times when using the N-SWEAT patch.

Please refer to Appendix G for guidance on when to refer to a burn center.

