17. Patients at risk for scarring, collagen vascular diseases, Hidradenitis suppurativa. Patients treated with isotretinoin may also experience severe scarring

TREATMENT APPROACH

Note: There is no difference in the treatment approach for the test vs. control groups. In the randomized cohort personnel are blinded to treatment assignments

INSPECTION	Final examination of the axilla to confirm freedom from any skin disease or irritation, including both visual and tactile assessment of any irregularities. Axilla must be free of abrasions, broken skin, or other conditions of concern. If both axillae do not meet this requirement, do not proceed with treatment.
IDENTIFICATION OF TREATMENT SITE	The target treatment area should be chosen by identifying a relatively flat area with the highest concentration of hair follicles; intended to maximize contact with the location of sweat production. For convenience, site may be marked.
PREP OF TREATMENT SITE	The subject's axilla (treatment site) will be cleaned with alcohol to ensure that no residual deodorant or other residue remains in the target treatment area. The area shall then be thoroughly dried.
PATCH APPLICATION	The clinician removes the release liner and applies the patch to the prepared and dried axillary area. The patch is held in place by the adhesive backing for the duration of the treatment, which is no longer than 3-minutes. Throughout the treatment period the clinician will observe the subject closely. If the subject experiences discomfort or pain that is significant (8 or greater pain level on a Wong-Baker FACES pain scale) the patch should be removed immediately even if it has been in place for less than 3 minutes.
POST TREATMENT	Immediately following patch removal, the treatment area will be cleansed thoroughly with water. A gauze pad soaked with water should be used to wipe the area a few times. This step should be repeated until the subject does not feel any residual effects. The patch should be placed into the disposal solution per instructions provided.
SECOND AXILLA	All the sequential steps above will be repeated for treatment of the second axilla in the same treatment visit.

RANDOMIZATION

RANDOMIZATION	Subjects in the randomized cohort will be randomized to one of two treatment groups in a 1:1 ratio to receive a single administration of N-SWEAT Patch or sham control patch in both axillae. The randomization will be stratified by HDSS 3 vs. 4 at baseline.

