4.3 Mechanism of Action

The N-SWEAT Patch is a non-invasive, topical patch designed to target and temporarily inactivate sweat glands using thermal energy, leading to reduced sweat production.

The N-SWEAT Patch is applied to the surface of dry, unabraded, intact skin by trained clinicians. The patch is activated by water released from sweat glands. When sweat (comprised of up to 99% water, Wilke et al. 2007) comes into contact with the patch, the sodium interacts with the water causing the patch to generate thermal energy. The amount and precise location of heat produced depends on the amount and location of sweat with which the patch comes into contact. In the absence of sweat (water), no thermal energy is generated.

The patch is applied for up to 3 minutes. Removal may occur prior to the 3-minute time point if the patient experiences pain or discomfort (as described in the Instructions for Use (IFU)).

The duration of the effect of the N-SWEAT patch is expected to be 6-8 weeks on average although early clinical data showed some patients maintained reduced sweat at 8-10 weeks. Duration time will be elucidated by this clinical study.

The N-SWEAT Patch is an Investigational Device and is limited by law for use only for subjects enrolled in an approved clinical study.

CANDESANT BIOMEDICAL	CLINICAL STUDY PROTOCOL SAHARA STUDY	Document #: CB-CLP-001 Revision: E
---------------------------------	---	---------------------------------------

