11.3 Minimization of Anticipated Risks

Risks associated with the N-SWEAT Patch are minimized by design and training. Risks are minimized under this protocol due to:

- Only operators with proper training and experience will use the device
- Clinician users will be given the opportunity to use their discretion and medical expertise throughout the treatment and appropriately respond to the patient's reaction to treatment
- Only certified personnel will dispose of the device
- Extensive non-clinical evaluation of the device (animal and bench top testing)
- The use of standard medical grade materials in the manufacture of the device

CANDESANT BIOMEDICAL	CLINICAL STUDY PROTOCOL SAHARA STUDY	Document #: CB-CLP-001 Revision: E
-------------------------	---	---------------------------------------

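### Protocol 8.7.2 sets two removal cut-offs in one sentence, so a reported pain score of exactly 8 permits patch removal but does not require it

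*Protocol*

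**What the plan says.** Protocol 8.7.2 schedules one pain reading during application: "Every 30 seconds, the subject shall report their pain level on a score of 1 to 10". The condition for mandatory removal follows: "If the subject reports a pain level greater than 8 or shows a 8 or higher using the Wong-Baker FACES pain scale". When it is met, the patch comes off at once, however long it has been on. Otherwise it comes off at 3 minutes.

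Other passages bear on the same decision:

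- **At placement (Protocol 8.7.2):** "If the subject reports any pain or uncomfortable sensation at the time of patch placement; the patch should be immediately removed".
- **Synopsis, Treatment Approach:** significant discomfort or pain is given a threshold on one scale only, "8 or greater pain level on a Wong-Baker FACES pain scale) the patch should be removed immediately". The synopsis also says: "Throughout the treatment period the clinician will observe the subject closely".
- **Protocol 4.3:** "Removal may occur prior to the 3-minute time point if the patient experiences pain or discomfort", with a pointer to the IFU.
- **Protocol 11.3:** "Clinician users will be given the opportunity to use their discretion and medical expertise throughout the treatment".
- **Status of 8.7.2:** it describes itself as an overview and adds that "it is critical to reference the IFU provided for additional treatment and handling details". The IFU is listed as Appendix K, without content in the documents available.

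**The concern.** Two thresholds are attached to one mandatory action, and they disagree about the value 8. The looser one belongs to the 1-to-10 score, which is the only reading scheduled while the patch is on. FACES is named as a trigger, but no timed FACES reading during application is written. Where the protocol wants FACES at a particular step it says so, as in 8.7.3 for the cleaning step.

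At stake is the clarity of a safety instruction. The device generates heat, and 8.7.2 itself warns of alkaline or thermal burns from excessive exposure. An operator who hears an 8 should be able to tell from the operative section whether removal is obligatory. Nothing in the documents explains why a spoken 8 should be handled more leniently than an 8 on FACES, so a drafting slip is the likeliest explanation.

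**Working it through.** No sample size, power or alpha figure is involved, so the check is logical: apply the 8.7.2 condition to each possible reading.

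**Inputs**

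- Numeric trigger (Protocol 8.7.2): score > 8 on a scale of 1 to 10.
- FACES trigger (Protocol 8.7.2): FACES ≥ 8.
- The two are joined by *or*, so either is enough.
- Synopsis trigger: FACES ≥ 8, with no 1-to-10 cut-off.

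**Application, after the moment of placement**

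| Reported score | FACES | Removal required by 8.7.2? |
|---|---|---|
| 9 or 10 | any | Yes, numeric trigger |
| 8 | 8 or higher | Yes, FACES trigger |
| 8 | below 8, or not shown | **No** |
| 1 to 7 | 8 or higher | Yes, FACES trigger |
| 1 to 7 | below 8, or not shown | No |

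The scores that satisfy ≥ 8 but not > 8 consist of the single value 8, so the third row is the whole gap. This does not depend on scores being whole numbers: an 8.5 would already exceed 8.

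**Do other passages close the third row?**

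- The placement rule in 8.7.2 is stricter than either cut-off, but it applies only when the patch goes on. It does not reach the later 30-second checks.
- Protocol 4.3 says that removal *may* occur, and 11.3 grants discretion. Both permit removal at 8; neither requires it.
- The synopsis requires removal at 8 on FACES. It gives no rule for a spoken 8 when FACES shows less or is not used.
- The SAP contains no removal rule.

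**After the change.** With ≥ 8 on both scales, the third row becomes *Yes* and no other row changes. The numeric cut-off then has the same value as the FACES cut-off in the synopsis.

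**The case against.** The other side has a fair case.

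- **The protocol largely covers it.** The synopsis already has the lower threshold, the clinician watches throughout, and 8.7.2 requires removal at FACES 8. The gap needs a subject who says 8 but does not show 8. The feasibility study in Protocol 3.3 reported acceptable procedural pain in all subjects, which gives no sign that this is common. This stands as a limit on size. It does not make removal mandatory in the third row.
- **The IFU may govern.** It may set its own threshold, staff are trained on the device, and the spoken score and FACES may be meant as one scale given in two ways. None of this can be checked here. It confines the point to the protocol wording, and a sound IFU would still leave 8.7.2 inconsistent with itself.
- **Removal is allowed at any pain level.** This is true, and it rules out some stronger readings.

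A reader might infer three such readings, none of which the documents support:

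1. *A measurable amount of extra exposure.* One could count the time left to the cap after each 30-second check. But a subject may voice an 8 between checks, the score may rise, FACES may reach 8, or the clinician may intervene. No frequency is given. The result would describe the check schedule, not an effect.
2. *Distortion of the SAP analyses of patch time and pain* (adverse-event subgroups in SAP 10, logistic models in SAP 11.1). Operators who hear a 5 or a 7 may also act differently and both comply, because 4.3 and 11.3 allow it. Most operator variation would come from that intended discretion and would remain after the edit.
3. *That the cut-off is the only rule for ending application early.* The placement rule and the permissive rule in 4.3 are stated too.

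**Conclusion.** The inconsistency is real. Protocol 8.7.2 gives one mandatory action two cut-offs that disagree at 8, and a reported 8 without a FACES 8 leaves removal optional. That is out of line with the threshold in the synopsis.

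The point is small: one score value, in an unknown number of subjects. The 3-minute cap is untouched, so the wording does not allow exposure beyond what was planned. The primary Cochran-Mantel-Haenszel test, the alpha level and the sample size are unaffected. It is a drafting correction to a safety instruction, worth making because it is specific and protective.

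The conclusion rests on reading 8.7.2 literally, on treating the spoken score and FACES as separate readings (as the *or* suggests), and on the protocol text alone, since the IFU cannot be seen.

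**What to change.** In Protocol 8.7.2, change *greater than 8* to *8 or higher*, so that 8 or higher on either the 1-to-10 score or FACES calls for immediate removal. State the same two-scale rule in the synopsis. Check the IFU against it and align whichever is out of step.

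The cost is one phrase in 8.7.2, matching synopsis wording, the IFU check and a short training note, handled as an amendment under Protocol 12.5 if the protocol is already in use. No new data are needed: patch duration and pain level during treatment are already summarized by group (SAP 8.2).

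The downside is shorter patch time in subjects who report exactly 8. Their number is not given. If heat is the main source of the pain (an assumption; the make-up of the sham is not described), they would be mostly in the active arm. The documents do not establish whether shorter patch time lowers response; SAP 11.1 plans to look at that relationship.

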8.7.3 Immediately Post-Treatment

Immediately following patch removal, the treatment area will be thoroughly cleansed with water. A gauze pad soaked with water should be used to wipe the area a few times. This step should be repeated until the subject does not feel any residual effects, such as tingling or stinging. The subject should be asked to report their pain level using the Wong-Baker FACES pain scale during cleaning. The treatment area will be visually assessed by the physician, photographs may be taken, and any noted Adverse Events (AEs) will be documented.

Assessment for Local Skin Reactions: The investigator will evaluate axillary application sites for skin irritation to determine if there is an immediate reaction to the investigational device. If present it should be documented in accordance with the Skin Erythema Assessment and the Clinical Signs/Symptom Descriptors (**Appendix B**).

8.7.4 Treatment of the Second Axilla

All steps (8.7.1 through 8.7.3) above will be repeated for treatment of the second axilla in the same treatment visit.

8.7.5 Subject Care and Medications

Subjects will be provided with instructions for post-treatment care. They will be instructed to rinse the area with water or cleanse with soap and water if they feel any discomfort. Deodorant will be provided for use during study participation.

CANDESANT BIOMEDICAL	CLINICAL STUDY PROTOCOL SAHARA STUDY	Document #: CB-CLP-001 Revision: E
-------------------------	---	---------------------------------------

Subjects may take over-the-counter pain medication as needed following treatment. Acetaminophen is recommended for pain control. Prescription strength pain medication is not expected to be necessary.

Subjects must refrain from using over-the-counter or prescription, prescription-strength, or clinical strength topical aluminum compounds or antiperspirants for the duration of study participation. An approved deodorant (without antiperspirant) will be provided at screening for convenience. Other deodorants without antiperspirant may be allowed; however, they must be approved by the investigator. Subjects must also refrain from using topical steroids or hair removal creams on the treatment areas.

Subjects must refrain from taking anticholinergic medications, beta blockers, calcium channel blockers, other systemic treatments, or medications that are known to cause heavy sweating during the study. If one or more of these medications or treatments are required, and in the opinion of the investigator would compromise study results, the subject will be followed for safety only. All relevant medications taken will be documented.

